4.10.4 Exploratory Evaluations

The exploratory efficacy variables will be based on a similar estimand to that described for the primary efficacy variable in Section 4.10.2.1, with the variable and population-level summary updated to be relevant to the exploratory efficacy variable specified.

The following exploratory endpoints will be summarised by treatment arm based on the FAS:

- Body weight changes in response to different doses of zibotentan and dapagliflozin in combination versus dapagliflozin 10 mg monotherapy, throughout the interventional period.
- Evaluation of changes in body fluid volume and distribution over time during the study. Change in total body water, extracellular fluid, and intracellular fluid volumes will be analysed.

Descriptive summary statistics, including change from screening, by treatment arm based on the ABPM set will be presented for:

- Mean 24-hour systolic and diastolic BP in ABPM at screening, Week 6 and Week 12.

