7 DISCONTINUATION OF STUDY INTERVENTION AND PARTICIPANT DISCONTINUATION/WITHDRAWAL

7.1 Discontinuation of Study Intervention

It may be necessary for a participant to permanently discontinue (definitive discontinuation) study intervention.

An individual participant **may be** discontinued from study intervention in the following situations:

- Participant decision. The participant is at any time free to discontinue treatment, without prejudice to further treatment.
- An AE that, in the opinion of the investigator or AstraZeneca, warrants discontinuation from further dosing.
- Severe non-compliance with the CSP.
- Safety reasons as judged by the investigator and/or sponsor where continued treatment may put participant at undue risk.

An individual participant **will be** discontinued from study intervention in the following situations:

- If BNP is increased > 100% from baseline AND is greater than 200 pg/mL; or if BNP is increased > 100% from baseline AND is greater than 400 pg/mL in a participant with atrial fibrillation.
- If the participant or male participant's partner becomes pregnant during the course of the study, investigational products should be discontinued immediately, and an AZ representative notified.
- Diabetic ketoacidosis: DKA including euglycemic DKA have been reported with use of dapagliflozin. Consider temporary interrupting study treatment if DKA is suspected. The participant should be promptly evaluated. If diabetic ketoacidosis is confirmed, investigational product(s) should be discontinued permanently. If diabetic ketoacidosis is not confirmed, restart of study intervention should be considered (see Section 7.1.1 for details).
- Symptomatic hypotension (defined as systolic BP < 90 mmHg OR diastolic BP < 60 mmHg with symptoms).
- eGFR reduction: investigational study products must be discontinued in case of confirmed eGFR reduction from baseline >50% and/or any confirmed decrease below 15 mL/min/1.73m².

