If an unexpected, acute decline in kidney function is observed, the participant should be promptly evaluated. Volume depletion, hypotension, intercurrent medical problems and concomitant drugs may cause increases in blood creatinine. Urinary tract infection and urinary obstruction should be considered. Several drugs may cause a decline in kidney function, especially non-steroidal anti-inflammatory drugs and certain antibiotics such as trimethoprim. If any drug is suspected of causing or contributing to worsening kidney function, their use should be reconsidered.
- More than 3% increase in weight (at least 2.5% must be from total body water as measured by bioimpedance) from start of treatment (Day 1).
- Heart failure.

Note that discontinuation from study intervention is NOT the same thing as a withdrawal from the study.

If study interventions are permanently discontinued, the participant will continue with the study visits and complete further evaluations as per the SoA (Table 1).

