3.2.2.2 Physical Examinations

Physical examination, and measurement of weight (analyses will be based on weight measured at the study site, not the home-based monitoring using the digital scales) and height will be conducted at the time points outlined in the SoA in [Appendix A: Schedule of Activities](#). For further information on the physical examinations refer to Section 8.2.1 in the clinical study protocol (CSP).

The only information relating to physical examinations that will be included in the CSR are any associated AEs, the recording and reporting of which are specified in Section 8.3.5 of the clinical study protocol (CSP).

Body weight must be taken and reviewed before continuing treatment at each visit as indicated in the SoA in [Appendix A: Schedule of Activities](#). Weight will be analysed as indicated in one of the exploratory objectives (the third bullet point in the table from Section 2.4).

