4.4 Handling of Dropouts or Missing Data

Summary statistics will be based on non-missing values. Information on how missing data will be handled for UACR is provided in Section 4.10.2. Missing safety data will generally not be imputed. However, safety assessment values (vital signs, laboratory assessments excluding urine albumin, urine creatinine and UACR) of the form “<x” (i.e. below the lower limit of quantification [LLOQ]) or “>x” (i.e. above the upper limit of quantification) will be imputed as “x” in the calculation of summary statistics but displayed as “<x” or “>x” in the listings. Measurements of urine creatinine, urine albumin and UACR which are displayed as “<x” will be imputed by using half of the “x” value, as this represents the LLOQ, justified by assuming that any value is equally likely between 0 and the LLOQ. These imputations are required in order to effectively calculate the geometric mean.

Partial or missing dates

If the start date of the concomitant medication or AE is missing, the following rules will be applied:

- If the year is missing, the year should be imputed as the year that participant received the first dose of study treatment.
- If the year is available and the month and day are missing, then impute the month as January and the day as 01.
- If the year and month are available and the day is missing, impute the day as 01 (the first day of the month).
- If any of the above puts the date before the date of first dose of study treatment, a conservative approach is followed, and the date is imputed using the date of first dose if the year matches the year of the date of first dose of study treatment when only the year is available or if the year and month matches the year and month of the date of first dose of study treatment when only the year and month are available.

If the stop date of the concomitant medication or AE is missing and there is an indication that there should be a stop date (ongoing flag marked as “N” for concomitant medication, outcome reported as resolved/fatal for AE), the following rules will be applied:

- If the year is missing, the year should be imputed as the year that participant received the last dose of study treatment.

- If the year is available and the month and day are missing, then impute the month as December and the day as 31.
- If the year and month are available and the day is missing, impute the day as the last day of the month (e.g. 28, 29, 30 or 31).

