4.10.2 Analyses of UACR Objectives

4.10.2.1 Primary Estimand for Primary Objective

The primary estimand is a hypothetical estimand such that the treatment effect is quantified in the optimal situation where any potential confounder is minimised. The analysis will be performed on the FAS. The endpoint being assessed is the change in log-transformed UACR from baseline to Week 12. Participants will be included in the analysis if they have a non-missing baseline and at least one non-missing post-treatment visit UACR measurement.

For the intercurrent events (ICEs), if a participant dies, prematurely discontinues study treatment, or uses prohibited medication, the UACR data are treated as missing after the event and no imputation will be performed. The summary measure being evaluated is the geometric mean reduction of UACR from baseline to Week 12.

The estimand is specified through the following definitions of population, variable, treatment condition, ICEs, and population-level summary:

Target population:	Defined by the inclusion/exclusion criteria.
Variable:	Change in log-transformed UACR from baseline to Week 12.
Treatment condition:	Zibotentan 1.5 mg combined with dapagliflozin 10 mg versus dapagliflozin 10 mg.
Intercurrent events:	Death, premature discontinuation from study treatment, or use of prohibited medication (Handled by hypothetical strategy i.e. UACR data are treated as missing after the event. Deaths are expected to be relatively few and will be handled in the context of missing data).
Population-level summary:	Difference in least squares mean change in log-transformed UACR from baseline to Week 12 between zibotentan 1.5 mg combined with dapagliflozin 10 mg and dapagliflozin 10 mg.

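### Body weight and body fluid are summarised from observed values only, while a stopping rule acts on the same variables, so means after the triggering visit understate on-treatment fluid gain

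*SAP*

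**What the plan says.** **Estimand.** SAP 4.10.4 opens: "The exploratory efficacy variables will be based on a similar estimand to that described for the primary efficacy variable in Section 4.10.2.1". It lists the variable and the population-level summary as the items to update. The handling of intercurrent events is not on that list. In SAP 4.10.2.1, after death, premature discontinuation or prohibited medication, "the UACR data are treated as missing after the event and no imputation will be performed".

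**Method.** SAP 4.10.4 continues: "The following exploratory endpoints will be summarised by treatment arm based on the FAS". The list covers body weight and body fluid. For fluid it adds "Change in total body water, extracellular fluid, and intracellular fluid volumes will be analysed", but names no model, contrast or interval. Protocol 9.4.2.3 likewise plans a summary. SAP 4.4 states "Summary statistics will be based on non-missing values". SAP 3.2.2.2 sends site-measured weight to the same place: "Weight will be analysed as indicated in one of the exploratory objectives".

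**Stopping.** Protocol 7.1 lists situations in which treatment will be discontinued. One is "More than 3% increase in weight (at least 2.5% must be from total body water as measured by bioimpedance", measured from Day 1. Another begins "If BNP is increased > 100% from baseline AND is greater than 200 pg/mL", with a higher limit in atrial fibrillation. Stopped participants continue with study visits.

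**Comparison variables.** SAP 4.10.3 gives BP and eGFR a similar estimand and an MMRM.

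**The concern.** The value being averaged helps decide who is absent from later averages. A participant who crosses the weight-and-water limit counts at that visit, must then stop, and drops out of the later means if post-stop values are treated as missing. The arm that retains more fluid loses more of its high values.

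An MMRM limits this because it uses what was seen before stopping. BP and eGFR have one. Weight and body fluid do not, although SAP 2.4 words their objectives as the combination versus dapagliflozin monotherapy.

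The variables matter. Fluid retention led to closure of both 5 mg arms (Protocol Appendix H, Amendment 2), and Protocol 4.3 rests the 1.5 mg dose partly on a prediction of less retention. The weight and water curves are where a reader would look for shifts below the event threshold.

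**Working it through.** The plan gives no figure for weight or body water, so there is none to reproduce. The stopping rule is from Protocol 7.1. Means, SDs, correlations and stopping rates are assumptions.

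**Step 1: identity.** For one arm at one visit, with *p* the proportion already stopped:

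observed mean − on-treatment mean = −*p* × (mean of stopped − mean of remaining).

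With an assumed gap of 3 percentage points of body weight:
- *p* = 5%: −0.05 × 3 = −0.15 points
- *p* = 10%: −0.10 × 3 = −0.30 points
- *p* = 20%: −0.20 × 3 = −0.60 points

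The arm difference shrinks when *p* × gap is larger in the zibotentan arm.

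**Step 2: simulation with the joint rule.** There were 400,000 participants per scenario, with weight change (%) at Weeks 1, 3, 6 and 12. Assumptions were weight SD 1.5 to 2.5 points, water SD 2.2, within-person correlation 0.7 and weight-water correlation 0.8. A participant stops after the first visit with weight gain above 3% and water gain of at least 2.5% of baseline weight. Later values are missing.

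| Weight SD | True Week 12 mean | Stopped before Week 12 | Observed mean | Shortfall |
|---|---|---|---|---|
| 1.5 | −1.0 | 1.4% | −1.04 | 0.04 |
| 1.5 | +0.5 | 7.7% | 0.33 | 0.17 |
| 2.0 | −1.0 | 4.8% | −1.15 | 0.15 |
| 2.0 | +0.5 | 14.2% | 0.13 | 0.38 |
| 2.5 | −1.0 | 8.0% | −1.28 | 0.28 |
| 2.5 | +0.5 | 18.3% | −0.07 | 0.57 |

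The two steps agree: at SD 2.0 the implied gaps are 0.38 / 0.142 = 2.7 and 0.15 / 0.048 = 3.1 points.

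**Step 3: arm difference.** The true difference is 0.5 − (−1.0) = 1.5 points. Observed means give 1.37, 1.28 and 1.21 at SD 1.5, 2.0 and 2.5:
- (1.5 − 1.37) / 1.5 = 9%
- (1.5 − 1.28) / 1.5 = 15%
- (1.5 − 1.21) / 1.5 = 19%

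A likelihood fit under missing at random, which is what an MMRM estimates, gives 1.49 to 1.50 on the same data.

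**Step 4: wider inputs.** Varying the assumed inputs further under the joint rule, a true 1.5 appears as 1.47 when few stop and as 1.04 at the other end, where about a quarter of the zibotentan arm stops. That is (1.5 − 1.47) / 1.5 = 2% to (1.5 − 1.04) / 1.5 = 31%. The likelihood fit returns 1.49 to 1.52.

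**Step 5: maximum on-treatment change.** In a similar simulation, the arm difference in mean maximum on-treatment change was 1.40 to 1.49, against about 1.50 with no stopping. Stopping barely affects this summary.

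**The case against.** **The missing-data rule is inferred.** SAP 4.10.2.1 speaks of UACR data, and SAP 4.10.4 says only that the estimand is similar. SAP 4.12.1 shows that the plan can restrict a summary explicitly: PK tables exclude visits after permanent discontinuation. SAP 4.10.4 has no such sentence, and it summarises body fluid over the whole study. This stands, so the rule should not be described as written. If post-stop values were kept instead, the means would mix on- and off-treatment values and answer a different question. Either reading needs wording.

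**Fluid events are analysed elsewhere.** A reader might infer that the plan hides fluid retention. The documents do not support that. SAP 3.2.2.7 uses the same weight, water and BNP limits as the stopping rule. SAP 4.11.5.1 reports crossings by arm with incidence rates, a relative risk against dapagliflozin with a one-sided 80% CI, and a listing. SAP 4.11.2 adds a fluid-overload table. This stands fully, but event counts do not correct the continuous means or show shifts below the threshold.

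**Only later visits are affected.** A reader might also infer that fluid gainers vanish altogether. They do not: the triggering value counts at its own visit.

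**No between-arm contrast of these means is planned.** True. Readers would form it from the by-arm summaries, because the objective is comparative.

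**The MMRM's recovery is built into the simulation.** Simulated stopping depends on modelled weight and water alone. Real stops also follow BNP, heart failure, symptomatic hypotension and judgement. This stands as a limit on the remedy.

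**Conclusion.** The concern holds for the continuous means of body weight and body fluid at visits after the triggering visit. It does not extend to the fluid events of special interest.

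If post-stop values are treated as missing, the plan's summaries understate on-treatment fluid gain, and do so more in the arm that retains more. That direction is relative to the on-treatment mean only. Fluid may fall after stopping, so adding post-stop values need not restore that mean.

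The size cannot be fixed from the documents. Under assumed inputs the arm difference shrinks by about 2% when few stop and by about 30% when a quarter of the zibotentan arm stops. Nothing in the documents shows that the retained doses would produce stopping at the upper end, so no single figure should be quoted as the expected bias.

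This is a cheap improvement to an exploratory analysis. It touches neither the primary result nor the stopping rule, on which no view is taken.

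**What to change.** In SAP 4.10.4:

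1. State that the discontinuation rule of the primary estimand applies to body weight and body fluid.
2. Analyse body weight, total body water and extracellular fluid with the MMRM specified for BP in SAP 4.10.3, using each variable's own baseline as covariate and the visits at which it is collected. Report visit-wise differences from dapagliflozin.
3. Add a by-arm summary of each participant's maximum on-treatment change.
4. Keep the raw means as description and show beside them the number stopped by each visit.

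The cost is SAP wording and a few more exploratory tables from a model already specified, with no new data. The MMRM assumes that observed values explain stopping. That is only partly true for stops due to BNP, heart failure or investigator judgement, and item 3 covers part of that gap.

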4.11 Safety Evaluation

All safety summaries and analyses will be based upon the Safety Analysis Set as defined in Section 4.6 and the on-treatment period as defined in Section 4.2.1, unless otherwise specified. Safety summaries will be presented by treatment arm.

Change from baseline will be calculated as the difference between the post-dose value at each time point and the last non-missing value prior to or on the same date as administration of the first dose of investigational products.

Individual safety and tolerability data will be provided in data listings and summarised as appropriate by treatment and overall. Continuous variables (laboratory parameters, ECG, and vital signs) will be summarised using descriptive statistics (n, mean, SD, minimum, median, and maximum) as appropriate by scheduled assessment time point. Where applicable, data will be summarised for the observed value, and for the corresponding change from baseline/screening. Categorical variables will be summarised in frequency tables (counts and percentage) as appropriate by scheduled assessment time point.

Changes from baseline in categorical data will be summarised using shift tables where appropriate.

4.11.1 Extent of Exposure

The extent of exposure (days) will be derived for zibotentan and dapagliflozin, combined, as follows:

$$\text{Duration of exposure (days)} = \text{Date of last dose} - \text{Date of first dose} + 1$$

The following extent of exposure summaries will be provided for zibotentan and dapagliflozin (combined):

- Duration of exposure (days)

- A summary of the duration of exposure to treatment (days) and cumulative exposure over time (≥ 1 day, ≥ 8 days, ≥ 22 days, ≥ 43 days, ≥ 64 days, ≥ 85 days), by treatment arm.
- Time on study (days) defined as:
 $Time\ on\ study\ (days) = (Date\ of\ last\ study\ assessment\ or\ Date\ of\ withdrawal) - Date\ of\ randomisation + 1.$

A listing for study drug administration according to protocol and the reason if the study drug administration is not according to protocol will be produced for the Safety Analysis Set.

A Kaplan-Meier figure for time to premature study drug discontinuation will be produced for the Safety Analysis Set. Time to premature study drug discontinuation (days) will be defined as:

- $Date\ of\ premature\ discontinuation\ from\ study\ drug - Date\ of\ first\ dose + 1$ for participants who prematurely discontinue study drug
- $Date\ of\ last\ visit\ day\ in\ the\ treatment\ period - Date\ of\ first\ dose + 1$ for participants who do not prematurely discontinue study drug but are lost to follow-up during the treatment period
- $Minimum(Withdrawal\ of\ consent\ date, Date\ of\ death, Date\ of\ Visit\ 7, Date\ of\ study\ day\ 86) - Date\ of\ first\ dose + 1$ for any other participants who do not prematurely discontinue study drug.

4.11.2 Adverse Events

Adverse events will be coded using MedDRA version 25.0 or a later version, if available.

AEs (and also separately SAEs) will be summarised by study treatment arm in incidence summaries by MedDRA SOC and PT. AEs will be assigned to the period where they start and will be summarised for the Safety Analysis Set. SAE collection will begin after the participant signs the informed consent document, and all AE collection will begin after the participant has received the first dose of the study intervention. The SAE/AE collection will last until the end of the participant's follow-up period.

All AEs will be listed and assigned to on/off treatment period as:

- Prior treatment: The SAE occurred before the first administration of study intervention. Only applicable for SAEs.
- On treatment: The AE occurred on the same date or after the first administration of study intervention until the earliest of: 28 days after last dose of zibotentan/placebo and/or dapagliflozin/placebo; end of study; lost to follow-up; and withdrawal of consent.
- Off treatment: The AE occurred more than 28 days after the last dose of study intervention.
- On + off treatment: The AE occurred on the same date or after the first administration of study intervention.

All AE summary tables will be presented for on treatment AEs and for on + off treatment AEs. Prior treatment and off treatment AEs will be listed but not summarised.

An overview of AEs will be presented for each treatment arm; the number and percentage of participants with any AE, any AE with outcome of death, any SAE, any DAE, any AE leading to study treatment dose interruptions, any AE leading to withdrawal from the study, and any AE possibly related to study treatment, as well as the number of individual occurrences in those categories.

The number and percentage of participants reporting AEs, SAEs and DAEs in each treatment arm will be tabulated by SOC and PT. If more than one event occurs with the same preferred term for

the same participant, the participant will be counted only once for that preferred term using the most severe and most related occurrence for the summarisation by intensity and by relationship to the study treatment.

The distribution of AEs by intensity and relationship to study treatment will be summarised by treatment arm.

The incidence of common ($\geq 5\%$ of participants in any treatment arm) AEs will be summarised by PT and treatment arm, sorted in decreasing overall (across treatments) frequency. For each participant and each AE, the worst intensity recorded will be attributed and used in the by-intensity summaries. Similarly, the worst causality will be attributed and used in the by-causality summaries. Multiple occurrences of an AE in the same participant will only be counted once overall. Non-serious AEs occurring in more than 5% of participants will be presented by treatment arm.

In addition, a tabulation of AEs, by PT, relevant for assessment of potential proarrhythmic effect will be provided based on the SMQ “Torsade de pointes/QT prolongation” (narrow and broad scope) and PT Seizure. A tabulation of AEs by PT will be provided for the SMQ “Haemodynamic oedema, effusions and fluid overload” (narrow scope).

Listings will be presented of participants with SAEs, AEs leading to discontinuation, and participants who died. A listing will be presented of participants with AEs, detailing whether these are SAEs, AEs leading to discontinuation, or result in death. Listings will include on- and off-treatment categorisation.

4.11.3 Deaths, Serious Adverse Events, and Adverse Events Leading to the Discontinuation of Study Intervention

The following summaries will be provided:

- A summary of the number and percentage of participants reporting an AE with outcome of death by treatment arm, SOC and PT
- A summary of key participant information for participants reporting an AE with outcome of death
- A summary of the number of SAEs reported by treatment arm, SOC and PT
- A summary of the number and percentage of participants reporting a SAE by treatment arm, SOC and PT
- A summary of key participant information for participants reporting a SAE
- A summary of the number and percentage of participants reporting a DAE by treatment arm, SOC and PT
- A summary of key participant information for participants reporting a DAE.

